## **4. CHANGES IN THE PLANNED ANALYSIS OF THE STUDY**

All analyses described in this TSAP are in accordance with the statistical methods described in the revised CTP.

While the CTP lists both the ANOVA and the descriptive analyses of the primary endpoint as part of the primary analysis, this TSAP focusses on the ANOVA as primary analysis and declares the descriptive analyses as exploratory analyses.

### **Assessment of COVID-19 Impact**

Due to the study interruption caused by the Covid-19 pandemic the decision was made to stop the study prematurely. This decision was based on the fact that the data from the 10 mg BI group was thought to be sufficient to adequately address the main study objective.

The study was permanently discontinued while the 15mg BI 1467335 group was still ongoing, due to lock down of the site. None of the subjects in the 15mg BI 1467335 group completed the tyramine challenge at visit 3. Therefore, TYR30 at steady state and the primary endpoint TSF are not available for the 15mg BI 1467335 group. As a consequence, the ratio of 15mg BI 1467335 (T2)/Placebo (R) (primary analysis of primary endpoint) can not be calculated. For safety evaluation all data will be used.

## **5. ENDPOINTS**

### **5.1 PRIMARY ENDPOINT**

Primary endpoint is the tyramine sensitivity factor (TSF), ratio of TYR30 at baseline and steady state, as defined in CTP Section 2.1.2.

[figure not shown]
### **5.2 SECONDARY ENDPOINTS**

#### **5.2.1 Key secondary endpoints**

Not applicable.

#### **5.2.2 Secondary endpoints**

Not applicable.

#### **5.3.2 Safety parameters**

Safety and tolerability of BI 1467335 and phenelzine will be assessed based on further safety parameters defined in Section 2.2.2.2 of the CTP:

- *Adverse events (including clinically relevant findings from the physical examination)*
- *Safety laboratory tests*
- *12-lead ECG*
- *Vital signs (blood pressure [BP], pulse rate [PR])*

## **5.4 OTHER VARIABLES**

### **5.4.1 Demographic and other baseline characteristics**

**CTP:** *At screening, the medical examination will include demographics, height and body weight, smoking and alcohol history, relevant medical history and concomitant therapy, review of inclusion and exclusion criteria, review of vital signs (BP, PR), 12-lead ECG, laboratory tests (including drug screening and pregnancy test in females), and a physical examination.*

Body mass index will be calculated as weight [kg] / height [m].

### **5.4.2 Treatment compliance and treatment exposure**

Treatment compliance will not be analysed as a specific endpoint, cf. Section 4.3 of the CTP.

Treatment exposure is defined as the total dose and number of doses of BI 1467335, phenelzine and tyramine per subject.

## 6. GENERAL ANALYSIS DEFINITIONS

### 6.1 TREATMENTS

For basic study information on treatments to be administered, assignment of treatment groups, and selection of doses, cf. Section 4 of the CTP.

All subjects will start by undergoing a "baseline" tyramine challenge receiving escalating daily doses of 5-700 mg tyramine until baseline TYR30 is reached. Baseline TYR30 is the tyramine dose causing an increase of systolic BP (SBP)  $\geq 30$  mmHg for at least 3 consecutive measurements compared with baseline SBP (baseline SBP is defined in [Section 6.6](#)).

Each subject is then planned to be treated with multiple doses of 10 mg or 15 mg BI 1467335 or matching placebo up to 39 days or with phenelzine up to 19 days. Treatment is to be stopped once TYR30 at steady state is achieved. Therefore, starting on Day 29 for BI 1467335 and placebo arms and on Day 8 for phenelzine, the tyramine challenge is to be repeated until TYR30 at steady state is reached.

For statistical analyses of AEs the following separate analysis phases will be defined for each subject:

Table 6.1: 1 Analysis phases for statistical analysis of AEs

Study analysis phase	Label	Start (inclusive)	End (exclusive)
Screening	Screening	Date of informed consent	Date/time of first administration of tyramine during Visit 2
On-treatment Tyramine screening challenge	Tyr screening	Date/time of first administration of tyramine during Visit 2	Date/time of first administration of BI 1467335, placebo or phenelzine respectively
On-treatment BI, Placebo or phenelzine	Placebo, 10 mg BI, 15 mg BI or Phen, respectively	Date/time of first administration of BI 1467335, placebo or phenelzine respectively	Date/time of first administration of tyramine during Visit 3 or 12:00 a.m. on day after last contact date whatever comes first
On-treatment BI + tyramine, Placebo + tyramine or phenelzine + tyramine	Placebo + Tyr, 10 mg BI + Tyr, 15 mg BI + Tyr or Phen + Tyr respectively	Date/time of first administration of tyramine during Visit 3	12:00 a.m. on day after last contact date

AE displays in CTR Section 15.3, Appendix 16.1.13.1.8.2 and Appendix 16.1.13.1.8.3 will present results for the on-treatment phase only.

In AE tables in CTR Section 15.3 (but not in Appendix 16.1.13.1.8.2 and Appendix 16.1.13.1.8.3 AE tables), the following totals will be provided in addition:

- **"Total on-trt"**, defined as the total over all on-treatment phases
- **"Total BI + Tyr"**, defined as the total over all on-treatment phases involving BI + Tyr

- "Total BI", defined as the total over all on-treatment phases involving BI

Vital signs and safety laboratory data will be analysed by treatment group (Placebo, Phen, 10 mg BI, 15 mg BI). Actual treatments displayed in addition will be based on the analysis phases of AEs (see [Table 6.1: 1](#)).

In summaries of disposition, demographics and baseline characteristics, a "Total" (across the treatment groups Placebo, 10 mg BI, 15 mg BI and Phen) will be presented additionally.

More details on the technical implementation of these analyses are provided in the ADS Plan of this TSAP.

## 6.2        IMPORTANT PROTOCOL DEVIATIONS

Consistency check listings (for identification of deviations from time windows) and a list of protocol deviations (e.g. deviations in drug administration, in blood sampling times, etc.) will be provided to be discussed at the Report Planning Meeting (RPM). At this meeting, it will be decided whether a discrepant data value can be used in the analyses or whether it must be corrected in the clinical database. Each protocol deviation must be assessed to determine whether it is an important PD (IPD). For definition of IPDs, and for the process of identification of these, refer to the BI reference document "Identify and Manage Important Protocol Deviations (IPD)" ([2](#)).

If any IPDs are identified, they are to be summarised into categories and will be captured in the decision log. Categories which are considered to be IPDs in this trial are defined in the integrated quality and risk management plan (IQRMP). If the data show other IPDs, the definition in the IQRMP will be supplemented accordingly by the time of the RPM.

IPDs will be summarized and listed. [Table 6.2: 1](#) below specifies which kind of IPDs could potentially lead to exclusion from which analysis set. The decision on exclusion of subjects from analysis sets will be made at the latest at the RPM, after discussion of exceptional cases and implications for analyses. If the data show other IPDs, this table will be supplemented accordingly by the time of the RPM.

Table 6.2: 1 Handling of IPDs

IPD code	IPD Category & Brief Description	Excluded from which analysis set
A1	Inclusion criteria not met	PPS
A2	Exclusion criteria not met	PPS
B1	Informed consent not available/not done	TS, PKS
B2	Informed consent too late	None
C1	Non-compliance	PPS, PKS
C2	Incorrect intake of trial medication	PPS, PKS
C3	Incorrect trial medication taken	PPS, PKS
D1	Prohibited medication use	PPS
D2	Improper washout of prohibited concomitant medication	PPS
E1	Certain violations of procedures used to measure primary endpoint data	PPS
F1	Certain violations of time schedule used to measure primary endpoint data	PPS
G1	PDs affecting safety and rights of subjects	None

### **6.3 SUBJECT SETS ANALYSED**

Subject sets will be used as defined in the CTP, Section 7.3.

Table 6.3: 1 Subject sets analyzed

		Subject set
Class of endpoint	TS	PPS
Primary endpoint		X
Safety parameters & treatment exposure	X	
Demographic/baseline endpoints	X	

## **6.5 POOLING OF CENTRES**

This section is not applicable, because the study was performed in only one centre.

[figure not shown]
## **6.6 HANDLING OF MISSING DATA AND OUTLIERS**

Data of screened subjects who were withdrawn from the trial prior to first administration of any study drug will not be reported in the CTR.

Data of subjects who failed to complete all periods of the study (dropouts or withdrawals) will be reported in the CTR as far as their data are available. All withdrawals will be documented and the reason for withdrawal reported in the CTR.

**CTP:** *It is not planned to impute missing values for safety parameters.*

One exception where imputation might be necessary for safety evaluation are AE dates. Missing or incomplete AE dates are imputed according to BI standards [\(3\)](#).

## **6.7 BASELINE, TIME WINDOWS AND CALCULATED VISITS**

Baseline is defined as the last available value assessed prior to first BI 1467335, placebo or phenelzine administration.

"Baseline" SBP used for comparison of TYR30 is defined as follows: Consider all SBP values within 35 min before tyramine administration on each tyramine testing day. If the SBP of the last 3 of these measurements are within a range of 10 mmHg, the mean of these 3 SBP values will be defined as baseline. If they are not within a range of 10 mmHg, the mean of all SBP values within 35 min before first tyramine administration will be defined as baseline. Baseline SBP is calculated prior to each tyramine testing day.

Time windows are defined in Section 6.1 of the CTP. Adherence to time windows will be checked at the RPM.

[figure not shown]
## 7. PLANNED ANALYSIS

The format of the listings and tables will follow the BI guideline "Reporting of clinical trials and project summaries" (6).

The individual values of all subjects will be listed. Listings will be sorted by treatment group subject number and visit (if visit is applicable in the respective listing). AE listings will be sorted by assigned treatment (see [Section 7.8.1](#) below for details). The listings will be contained in Appendix 16.2 (SDL) of the CTR.

The following standard descriptive statistical parameters will be displayed in summary tables of continuous variables:

N	number of non-missing observations
Mean	arithmetic mean
SD	standard deviation
Min	minimum
Median	median
Max	maximum

Tabulations of frequencies for categorical data will include all possible categories and will display the number of observations in a category as well as the percentage (%) relative to the respective treatment group. Percentages will be rounded to one decimal place. The category missing will be displayed if and only if there actually are missing values. Percentages will be based on all subjects in the respective subject set whether they have non-missing values or not.

### 7.1 DEMOGRAPHIC AND OTHER BASELINE CHARACTERISTICS

Only descriptive statistics are planned for this section of the CTR.

## **7.2 CONCOMITANT DISEASES AND MEDICATION**

Concomitant diseases will be coded according to the most recent version of MedDRA. Concomitant medication will be coded according to the most recent version of the World Health Organisation – Drug Dictionary. Concomitant non-drug therapies will be coded according to the most recent version of MedDRA.

A medication will be considered concomitant, if it

- is ongoing at the time of first study drug administration, or
- starts within the analysis phase of the respective treatment (see [Section 6.1](#) for a definition of treatments and analysis phases).

The relevance of the concomitant therapies to the evaluation of PK will be decided no later than at the RPM.

Only descriptive statistics are planned for this section of the CTR.

## **7.3 TREATMENT COMPLIANCE**

Treatment compliance will not be analyzed as a specific endpoint. Any deviations from complete intake will be addressed in the Report Planning Meeting (cf. [Section 6.2](#)) and described in the CTR.

## **7.4 PRIMARY ENDPOINTS**

### **7.4.1 Primary analysis of the primary endpoint**

Primary analysis of the primary endpoint will be performed as defined in Sections 7.3.1 of the CTP.

The statistical model for the primary analysis defined in the CTP is an analysis of variance (ANOVA) model on the logarithmic scale including "treatment" as fixed effect. The model will include all three treatments at the same time, i.e., including data from treatments T1, C and R in the same analysis. The difference in TSF will be estimated by the ratios of the geometric means of

- 10 mg BI 1467335 (T1)/ Placebo (R)
- Phenelzine (C)/ Placebo (R)

of the primary endpoint.

### **7.4.2 Sensitivity analysis, subgroup analysis, exploratory analysis of the primary endpoint**

The primary endpoint will also be assessed descriptively. Summary statistics, by treatment, will be presented for TSF, TYR30 at baseline and TYR30 at steady state.

[figure not shown]
## **7.5 SECONDARY ENDPOINTS**

### **7.5.1 Key secondary endpoints**

This section is not applicable as no key secondary endpoint has been specified in the protocol.

### **7.5.2 Secondary endpoints**

This section is not applicable as no secondary endpoint has been specified in the protocol.

## **7.6.2 Safety parameters**

Safety endpoints and tolerability will be analysed as described in [Section 7.8](#) of this TSAP.

## **7.7 EXTENT OF EXPOSURE**

Descriptive statistics are planned for this section of the report.

## 7.8 SAFETY ANALYSIS

All safety analyses will be performed on the TS.

### 7.8.1 Adverse Events

AEs will be coded with the most recent version of MedDRA.

The analyses of AEs will be descriptive in nature. All analyses of AEs will be based on the number of subjects with AEs and not on the number of AEs.

For further details on summarization of AE data, please refer to "Analysis and Presentation of Adverse Event Data from Clinical Trials" ([7](#)) and "Handling of missing and incomplete AE dates" ([3](#)).

The analysis of AEs will be based on the concept of treatment emergent AEs. That means that all AEs will be assigned to screening, on-treatment or follow-up phases as defined in [Section 6.1](#). AEs will be analysed based on actual treatments, as defined in [Table 6.1: 1](#).

An overall summary of AEs will be presented. This overall summary will comprise summary statistics for the class of other significant AEs according to ICH E3 ([8](#)) and for the class of AESIs.

**CTP:** *The following are considered as AESIs:*

- *Hepatic injury*  
*A hepatic injury is defined by the following alterations of hepatic laboratory parameters:*
  - *An elevation of AST (aspartate transaminase) and/or ALT (alanine transaminase)  $\geq 3$ -fold ULN combined with an elevation of total bilirubin  $\geq 2$ -fold ULN measured in the same blood sample, or*
  - *Aminotransferase (ALT, and/or AST) elevations  $\geq 10$  fold ULN*

The investigator had to classify on the eCRF whether an observed AE was an AESI or not.

According to ICH E3 ([8](#)) AEs classified as "other significant" need to be reported and will include those non-serious and non-significant AEs

- (i) which are marked haematological or other lab abnormalities, or
- (ii) which were reported with "action taken = discontinuation" or "action taken = reduced", or
- (iii) which lead to significant concomitant therapy as identified by the Clinical Monitor/Investigator at a Medical Quality Review Meeting.

The frequency of subjects with AEs will be summarised by treatment, primary SOC and preferred term. AEs which were considered by the investigator to be drug related will be summarised separately. Separate tables will also be provided for subjects with SAEs, subjects with AESIs and subjects with other significant AEs (according to ICH E3 ([8](#))). AEs will also be summarized by maximum intensity.

The SOCs and preferred terms within SOCs will be sorted by descending frequency over all treatment groups.

For disclosure of AE data on ClinicalTrials.gov, the frequency of subjects with non-serious AEs occurring with an incidence of greater than 5 % (in preferred terms) will be summarised by treatment, primary SOC and preferred term. The frequency of subjects with SAEs will also be summarised.

For disclosure of AE data in the EudraCT register, the frequency of AEs, the frequency of non-serious AEs with an incidence of greater than 5 % (in preferred terms) and the frequency of SAEs will be summarized.

For support of lay summaries, the frequency of subjects with drug-related SAEs will be summarized by treatment, primary SOC and preferred term.

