From Day 29, for the BI treatment and placebo arms, and Day 8 for the phenelzine arm, tyramine challenge will be repeated with escalating doses from 5 mg to 700 mg until TYR30 has been established. Concomitant to the tyramine challenge subjects will continue with the intake of their assigned medication, resulting in a maximum treatment duration of up to 19 days (on Day 19 intake of phenelzine only in the morning) for the phenelzine dose group and up to 39 days for the BI 1467335 dose groups.

The study will start with subjects of the phenelzine group. After completion of at least 8 subjects of the phenelzine group, subjects of all dose groups may enter the study.

An overview of all relevant trial activities is provided in the [Flow Chart](#). For visit schedule and details of trial procedures at selected visits, refer to [Sections 6.1](#) and [6.2](#), respectively.

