### 7.3.4 Safety analyses

Safety will be analysed based on the assessments described in [Section 2.2.2.2](#). All treated subjects (TS, refer to [Section 7.2](#)) will be included in the safety analysis. Safety analyses will be descriptive in nature and based on BI standards. No hypothesis testing is planned.

For all analyses, the treatment actually administered (= treatment at onset) to the subject will be used (any deviations from the randomised treatment will be discussed in the minutes of the Report Planning Meeting).

Treatments will be compared in a descriptive way. Tabulations of frequencies/proportions will be used to evaluate categorical (qualitative) data, and tabulations of descriptive statistics will be used to analyse continuous (quantitative) data.

Proprietary confidential information © 2020 Boehringer Ingelheim International GmbH or one or more of its affiliated companies

Measurements (such as ECG, vital signs, or laboratory parameters) or AEs will be assigned to treatments (see [Section 4.1](#)) based on the actual treatment at the planned time of the measurement or on the recorded time of AE onset (concept of treatment emergent AEs). Therefore, measurements planned or AEs recorded prior to first intake of trial medication will be assigned to the screening period, those between first trial medication intake and end of REP (see [Section 1.2.4](#)) will be assigned to the treatment period. Events occurring after the REP but prior to next intake or end of trial termination date will be assigned to 'follow-up'. In case of two or more treatments, the follow-up will be summarized according to the previous treatment. These assignments including the corresponding time intervals will be defined in detail in the TSAP. Note that AEs occurring after the last per protocol contact but entered before final database lock will be reported to Pharmacovigilance only and will not be captured in the trial database.

Additionally, further treatment intervals (analysing treatments) may be defined in the TSAP in order to provide summary statistics for time intervals, such as combined treatments, on-treatment totals, or periods without treatment effects (such as screening and follow-up intervals).

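### AE tables compare crude percentages of subjects over phases of unequal length (28 days on BI or placebo, 7 on phenelzine) and show no time at risk

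*SAP*

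**What the plan says.** SAP 7.8.1 sets the measure: "All analyses of AEs will be based on the number of subjects with AEs and not on the number of AEs". It sets the layout too: "The frequency of subjects with AEs will be summarised by treatment, primary SOC and preferred term". Treatment here means actual treatment by the phases of Table 6.1: 1 in SAP 6.1. SAP 7 has categorical tables show counts "as well as the percentage (%) relative to the respective treatment group". Protocol 7.3.4 gives the purpose: "Treatments will be compared in a descriptive way".

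In Table 6.1: 1 the drug-alone phase starts at the first dose of BI 1467335, placebo or phenelzine. It ends at: "Date/time of first administration of tyramine during Visit 3 or 12:00 a.m. on day after last contact date whatever comes first". Protocol 3.1 fixes when the second tyramine challenge starts: "From Day 29, for the BI treatment and placebo arms, and Day 8 for the phenelzine arm".

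On the early stop, SAP 4 reports: "The study was permanently discontinued while the 15mg BI 1467335 group was still ongoing, due to lock down of the site". It adds that no 15 mg subject completed the Visit 3 challenge and that all data are kept for safety. SAP 6.1 defines a Total BI column over all BI phases and a single placebo group.

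SAP 5.4.2 defines exposure as total dose and number of doses, without time at risk and without naming placebo. SAP 7.7 plans descriptive statistics for it, separately from the AE tables.

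**The concern.** The percentage of subjects with at least one AE rises with the length of observation. When columns that cover different lengths stand side by side, the shorter one shows a lower percentage even if the daily risk is the same. The drug-alone phase differs in length by design, so this distortion is built into a comparison the protocol announces. It flatters phenelzine against both BI 1467335 and placebo, and could hide a real excess on phenelzine.

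The early stop adds a second, unplanned source of unequal time. The SAP is dated after the stop and describes it, but the AE section gives no means of seeing how long each arm was observed.

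**Working it through.** **1. Planned phase lengths.** Protocol 3.1 states 28 days of BI or placebo and 7 days of phenelzine before the second challenge. The flow charts agree. The first challenge day opens at 670 h (BI, placebo) or 166 h (phenelzine) at 06:00, and tyramine follows two hours later.

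- BI, placebo: (670 + 2)/24 = 672/24 = 28.0 days
- Phenelzine: (166 + 2)/24 = 168/24 = 7.0 days
- Ratio: 28/7 = 4

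**2. Effect on the crude percentage.** The documents give no AE rate for this trial. Assume one constant rate λ in all arms, and let p be the proportion of subjects with an AE over 28 days:

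λ = −ln(1 − p)/28; P(AE within 7 days) = 1 − exp(−7λ) = 1 − (1 − p)^(1/4)

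| 28-day % (assumed) | 7-day % | Ratio | First AEs per 100 subject-days, both arms |
|---|---|---|---|
| 20 | 5.4 | 3.7 | 0.80 |
| 40 | 12.0 | 3.3 | 1.82 |
| 60 | 20.5 | 2.9 | 3.27 |

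The last column is 100λ. It is the same for both phase lengths, so a rate removes the artefact under this assumption. Conversely, a phenelzine rate four times the BI or placebo rate would give the same crude percentage, because 4λ × 7 = λ × 28.

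**3. Is this visible in small arms?** With the planned 14 phenelzine and 16 BI 10 mg subjects and identical rates, exact binomial enumeration gives the chance that phenelzine shows the lower percentage. It is 86%, 98% and 99.6% at 28-day levels of 20%, 50% and 80%. With equal phase lengths it would be 48% to 52%.

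**4. Where the problem does not arise.** The drug + tyramine phase runs from 08:00 on the first challenge day to midnight after last contact. Take last contact as the end-of-trial visit (Day 41 to 51 for BI and placebo, Day 21 to 31 for phenelzine):

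- BI, placebo: 41 − 28 − 8/24 = 12.7 days, up to 51 − 28 − 8/24 = 22.7 days
- Phenelzine: 21 − 7 − 8/24 = 13.7 days, up to 31 − 7 − 8/24 = 23.7 days

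These are nearly equal. Within Dose Group 1, 10 mg and placebo follow the same planned schedule.

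**5. The 15 mg group.** Its time on treatment is not given. A subject who began the challenge without finishing it has a full 28-day drug-alone phase. For a subject who never began it, the phase runs to the day after last contact, so time off drug can count. For assumed phases of 7, 14, 21, 28 and 40 days, a rate giving 50% over 28 days reads 15.9%, 29.3%, 40.5%, 50.0% and 62.9%. The distortion could therefore go either way.

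**The case against.** Counting subjects with AEs is a standard display, the safety analysis is descriptive with no testing, and phenelzine is an open-label, non-randomised control chosen for its effect on TSF. Numbers of doses are summarised and individual values are listed, so short exposure can be found. SAP 7.8.1 also refers to an internal AE standard that is not available here and may include time-based displays. Rates need a roughly constant hazard. All of this limits the weight of the point. It does not supply time at risk next to the percentages being compared.

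Four stronger readings are tempting, and the documents do not support them.

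- *Crude percentages understate AEs at 15 mg.* Neither size nor direction can be derived, as step 5 shows.
- *Subjects never challenged at 15 mg sit in the 15 mg BI + Tyr denominator.* A reader might infer this from SAP 7: "Percentages will be based on all subjects in the respective subject set whether they have non-missing values or not". That is a general rule on missing values. SAP 7.8.1 specifically analyses AEs by actual treatment, and a subject without a Visit 3 tyramine dose has no such phase.
- *Dose Group 2 placebo was cut short to the same extent as 15 mg.* This is plausible, but no durations are given.
- *Safety is the only 15 mg result left.* The primary endpoint is unavailable at 15 mg, but protocol 2.1.1 also lists exploratory pharmacokinetics as an objective.

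**Conclusion.** The point holds for the drug-alone phase, in comparisons of phenelzine with BI 1467335 or placebo. The planned lengths differ 4 to 1. At an identical constant rate, with 20% to 60% of subjects affected over 28 days, phenelzine would show about 5% to 20%, roughly 3- to 4-fold lower. The rate range and the constant hazard are assumptions: early clustering of AEs narrows the gap, and late onset widens it.

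For 15 mg the conclusion is weaker. Its time at risk may differ from that of the other arms, and it carries into Total BI. Any Dose Group 2 placebo subjects are merged with Dose Group 1 placebo. The tables would not reveal how much this matters or in which direction.

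No test and no primary result is affected. This is an inexpensive improvement to how the safety tables can be read.

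**What to change.** In SAP 6.1 and 7.8.1, add for each phase, beside n (%):

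- the number of subjects who entered the phase, stated as the denominator;
- subject-days at risk, counted from phase start to first AE or phase end;
- subjects with a first AE per 100 subject-days at risk.

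Show Dose Group 2 placebo separately as the concurrent comparator for 15 mg, in addition to the pooled placebo column. A common Day 1 to Day 7 window would be a useful supplement, since it compares arms over equal time without a hazard assumption.

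The cost is SAP wording and extra table columns. Phase dates are already derived for Table 6.1: 1, AE onset dates are already recorded, and the existing percentages stay. The downside is that the rates assume a roughly constant hazard and will be imprecise in arms planned at 14 to 16 subjects. Both limits should be stated in a table footnote.
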